- 9) Other concomitant drugs: drug name, reason for use, administration route, dose, and administration period
- 10) Drugs/combination therapies other than medication for ulcerative colitis

Presence or absence of drugs/combination therapies other than medication for ulcerative colitis, name of therapy, and therapeutic duration

11) Presence or absence of onset of tuberculosis or serious respiratory disorders

Examination day, imaging diagnostic method, abnormal findings, and abnormality

12) Mayo Score

Examination day (at initiation of administration, week 4, 8, 16, 24, 32, and 52 of administration, and discontinuation of administration)

13) CRP

Examination day (at initiation of administration, week 4, 8, 16, 24, 32, and 52 of administration, and discontinuation of administration)

14) Endoscopic finding

Examination day (at initiation of administration, week 24, 52 of administration, and discontinuation of administration)

15) Overall improvement (judgment by attending physician)

Judgment day (at week 52 of administration or at discontinuation)

Overall improvement (Remarkably effective, Effective, Ineffective, and Unevaluable)

16) Adverse events (including abnormal change in laboratory values)

Occurrence of adverse events, name of adverse events, onset day, seriousness, causal relationship to this drug, suspected drug(s), symptom and clinical course, treatment (with this drug or symptomatic treatment), outcome, laboratory values (if abnormally changed), and judgment reason if no causality

17) Key survey items

Infection, tuberculosis, malignant tumor, administration site reaction, autoimmune disease, pancytopenia, demyelinating disorders, congestive cardiac failure, and interstitial pneumonia

18) Measurement of anti-adalimumab antibody

If measurement of anti-adalimumab antibody is judged to be necessary

9. Analysis and Methods

- (1) Analytical items
 - 1) Patient population
 - 1. No. of enrolled patients
 - 2. No. of CRFs recovered
 - 3. Safety evaluation set
 - 4. Efficacy evaluation set
 - 2) Safety
 - 1. List of adverse reactions and infections
 - 2. Factors likely to affect the safety

- Incidence of adverse reactions by patient background
- Presence or absence of the use experience with anti-TNFα preparation and the relationship of safety.
- Safety in Long-Term administration
- Relationship of safety when anti-adalimumab antibody was determined
- Safety in patients conducting self-administration

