	Conducted: When "HBs antibody test" in the survey form was
	conducted (If "conducted" was not checked but the test results were
HBs antibody test	provided, it should be regarded as "conducted")
	Not conducted: When "HBs antibody test" in the survey form was
	not conducted
	Unknown/not provided: other than the above
	Conducted: When "HBc antibody test" in the survey form was
HBc antibody test	conducted (If "conducted" was not checked but the test results were
	provided, it should be regarded as "conducted")

Data name	Derivation and calculation methods
	Not conducted: When "HBc antibody test" in the survey form was
	not conducted
	Unknown/not provided: other than the above
	Conducted: When "HBV-DNA quantification assay" in the survey
	form was conducted (If "conducted" was not checked but the assay
HBV-DNA	results were provided, it should be regarded as "conducted")
quantification assay	Not conducted: Not conducted: When "HBV-DNA quantification
	assay" in the survey form was not conducted
	Unknown/not provided: other than the above
	Conducted: When either of "Tuberculin test" or "IGRA" was
	conducted (If "conducted" was not checked but the results were
Tuberculin test or IGRA	provided, it should be regarded as "conducted")
Tuberculin test of IGRA	Not conducted: When neither "Tuberculin test" nor "IGRA" was
	conducted
	Unknown/not provided: other than the above
	When the first administration date of Humira is 1 and a day before
	the first administration date is -1, the patients who underwent chest X
Chest X ray test	ray test should have a record in which the chest X ray test was
	conducted between -90 and 1. Of note, the data in the survey form
	shall be used.
	When the first administration date of Humira is 1 and a day before
	the first administration date is -1, the patients who underwent
Chest CT test	thoracic CT test should have a record in which the CT test was
	conducted between -90 and 1. Of note, the data in the survey form
	shall be used.
	When the first administration date of Humira is 1 and a day before
	the first administration date is -1, the patients who underwent any
Other imaging	other imaging should have a record in which the imaging was
	conducted between -90 and 1. Of note, the data in the survey form
	shall be used.
	Conducted: When either "chest X ray" or "CT test" in the survey
Chest X ray or CT test	form was conducted (If "conducted" was not checked but the test
	results were provided, it should be regarded as "conducted")

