Tuberculosis test	Conducted: when both "Tuberculin test or IGRA" and "Chest X ray
	or CT test" were conducted
	Not conducted: other than the above
	Conducted: when "HBV-DNA quantification assay" in the survey
Hepatitis B test	form was conducted, or
	when the results are negative in HBs antigen test, HBs antibody test,
	and HBc antibody test.
	Not conducted: other than the above

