Sex, pregnancy/nursing, race, age (year), body weight (kg), BMI (kg/m²), duration of illness (year), indication (registration form), allergy history, smoking history, detailed classification of smoking history, tuberculosis test, hepatitis B test, complication, detailed classification of complications, complication/others, medical history, detailed classification of medical history, prior medication for colitis ulcerative, detailed classification of prior medication for colitis ulcerative, treatment for colitis ulcerative, detailed classification of medical product, concomitant medication for colitis ulcerative, detailed classification of "with" biological product, concomitant medication for colitis ulcerative, detailed classification of concomitant medication for colitis ulcerative, concomitant treatment for colitis ulcerative, detailed classification of the disease site "colon", site of disease by type, partial Mayo score, CRP

Note: For the discontinuation reasons for the detailed classification of pregnant/nursing or 'using' biological products", calculate the percentage to the aggregation item right above the item. For other items, calculate the percentage to the number of target patients.

Overlapped aggregation may occur in the detailed classification of complications and complication of other classification, detailed classification of medical history, detailed classification of prior medications for colitis ulcerative, detailed classification of prior treatment for colitis ulcerative, detailed classification of 'using' biological products', detailed classification of concomitant medications for colitis ulcerative, detailed classification of concomitant treatment for colitis ulcerative, and the detailed classification of site of disease for colitis ulcerative and the site of

disease "colon".

"1.13 Incidence of self-administration error"

Patients for analysis: patients in the safety analysis group

Analysis objective: to show the distribution status for presence/absence of self-administration and the detailed classification of self-administration.

Analysis item: calculate the number of patients in the analysis groups.

Calculate the number of patients per "self-administration" defined in "11. How to stratify data" and the percentage to the number of patients in the analysis groups.

In addition, calculate the number of patients per "self-administration error" and the percentage to the patients 'with' self-administration.

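### The SAP's tuberculosis-test variable is built from a chest-imaging item that lacks the Day -90 to 1 window set for chest X-ray and chest CT

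*SAP*

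**What the plan says.** SAP 10.1 (General) treats chest imaging in two ways.

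- **Separate items.** *Chest X ray test* requires a record that the test was "conducted between -90 and 1. Of note, the data in the survey form" being the stated source. *Chest CT test* follows the same rule: a patient with "thoracic CT test should have a record in which the CT test was" done in that same window. The first dose is Day 1 and the day before it is Day -1.
- **Combined item.** *Chest X ray or CT test* is conducted "When either 'chest X ray' or 'CT test' in the survey" form was conducted. It has its own fallback for an unticked box: if "results were provided, it should be regarded as 'conducted". Everything else is not conducted. The row gives no date and does not refer to the two windowed items.

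*Tuberculosis test* is then defined as "Conducted: when both 'Tuberculin test or IGRA' and 'Chest X ray" or CT were conducted, so it draws on the combined item. Its other half reads "Conducted: When either of 'Tuberculin test' or 'IGRA' was" conducted, also without a date.

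The variable is used in two places in SAP 13.1. Table 1.12 (patient backgrounds) includes the run "tuberculosis test, hepatitis B test, complication". Listing 1.4 prints it next to the X-ray and CT fields for each patient.

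On data collection, protocol 8(3) item 11 is headed "Presence or absence of onset of tuberculosis or serious respiratory disorders" and records examination day, imaging method and findings. Protocol 6(3) has the CRF completed at Week 52 or at discontinuation.

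**The concern.** One SAP gives two rules for the same films, and the summary variable uses the looser one. A film taken months into treatment does not meet the X-ray or CT item. It does satisfy the imaging half of *Tuberculosis test*.

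Tuberculosis is a priority item in the protocol and SAP, and its incidence is part of the sample-size rationale. A reader of Table 1.12 may well take the proportion tested as describing work-up around the start of treatment. At stake are the accuracy of that proportion and the internal consistency of listing 1.4.

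**Working it through.** The plan states no figure for this variable, so there is none to reproduce. The check compares the definitions.

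**Step 1: the rules as logic.** Let S = tuberculin test or IGRA conducted; W = a chest X-ray or chest CT record in Day -90 to 1; A = any X-ray or CT conducted, or a result given, in the survey form at any date.

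- SAP rule: tested = S and A.
- Rule consistent with the window: tested = S and W.

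If both items read the same form, W implies A. The two rules then differ only for patients with S and A but not W, and all of these move from not conducted to conducted. The error has one direction.

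**Step 2: example patients.**

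| Patient | X-ray or CT item (windowed) | Combined item | Tuberculosis test, SAP | Tuberculosis test, windowed |
|---|---|---|---|---|
| IGRA; CT on Day -30 | CT yes | conducted | conducted | conducted |
| IGRA; only a CT on Day 140 | neither | conducted | conducted | not conducted |
| IGRA; only an X-ray on Day -100 | neither | conducted | conducted | not conducted |
| No tuberculin test or IGRA; CT on Day 140 | neither | conducted | not conducted | not conducted |

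In the second row, listing 1.4 contradicts itself within one patient. The third row is a pre-treatment film and differs only because of the SAP's 90-day limit. The fourth shows that a late film alone is not enough.

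**Step 3: can out-of-window films be on the form?** CRF item 11 collects imaging by examination day under onset of disease, and the CRF is completed at the end of observation. A Day -90 to 1 filter on survey-form records would also do nothing if the form held only films from that window. Both points suggest yes. Neither proves it, because the blank form is not among the documents.

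**Step 4: size.** Excess proportion = a × b, where a = share of patients with S but not W, and b = share of those with a film outside the window. The documents give neither. Since b lies between 0 and 1, the excess lies between 0 and a. For scale only, assume a = 10% of 1500, which is 150 patients:

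- b = 0: no patients.
- b = 20%: 150 × 0.20 = 30 patients, 30/1500 = 2 points.
- b = 50%: 150 × 0.50 = 75 patients, 75/1500 = 5 points.

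The values of a and b are assumptions, and b here includes films before Day -90.

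**Step 5: reach.** *Tuberculosis test* is not among the factors tested in tables 2.9 or 3.4, and 3.4.1 takes its factors from 3.4. (Medical history of tuberculosis is in those lists, but it is a different variable.) No p-value depends on it.

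**The case against.** The strongest reply is that the combined item may read a different part of the form. Its wording, with an unticked box rescued by an entered result, matches the hepatitis B and tuberculin/IGRA rows, whereas CRF item 11 lists no such box. Protocol 8(2) puts tuberculin, QuantiFERON, chest X-ray and CT together on the enrollment form, which is completed once treatment is decided. The SAP takes the hepatitis B tests from the survey form although the protocol's CRF list does not include them, so the SAP's survey form may contain a pre-treatment screening block. If the combined item reads only that block, no on-treatment film enters. This is possible and makes the practical effect conditional. It does not remove the defect, because the SAP does not restrict the row to such a block and a programmer following the text would apply no date.

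Three further points stand:

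- Table 1.12 also holds concomitant medication and therapy, which are defined by overlap with dosing. Placement there does not by itself make the variable pre-treatment.
- A film before Day -90 is still pre-treatment, so not every reclassified patient is an error of substance.
- Listing 1.4 shows each component beside the tuberculosis flag. At the SAP's planning incidence (1/177), 1500 × 1/177 is about 8.5 cases, few enough to inspect one by one.

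A reader might infer that the definition hides a link between omitted screening and tuberculosis. The documents do not support that: no planned table relates the two, and a missing film in the window stays visible in listing 1.4.

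**Conclusion.** The inconsistency holds on the text: the combined chest-imaging item drops the window that the SAP applies to its parts, and *Tuberculosis test* inherits the gap. It can only raise the proportion reported as tested, and it can make listing 1.4 contradict itself for a patient. It affects one row of Table 1.12 and one flag in listing 1.4, and no planned test.

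The conclusion assumes that the combined item is programmed as written, that the survey form holds some films outside Day -90 to 1, and that the thoracic CT field of listing 1.4 is the windowed chest CT item of 10.1. The size cannot be derived from the documents; the 2 and 5 points above are only what assumed shares would give. Nor do the documents support the inference that nearly every unscreened tuberculosis case would read as screened: they give no rate of on-treatment imaging, and a tuberculin test or IGRA is still required.

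**What to change.** In SAP 10.1, define *Chest X ray or CT test* as conducted when *Chest X ray test* or *Chest CT test* is met under the existing Day -90 to 1 rule, and derive *Tuberculosis test* from that. Leave the tuberculin/IGRA component as it is, since the documents show no date for it and a window might not be programmable.

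The cost is one sentence in the SAP and a change to one derivation, using imaging dates that the SAP already needs. There are two downsides. The reported proportion tested may be slightly lower. A patient whose only film predates Day -90 is counted as not conducted, which is consistent with the SAP's own window but should be footnoted in Table 1.12.

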9.2. Descriptive statistics

The following will be calculated for categorial data and quantitative data.

Data type	Item to be calculated		
	Number of patients, percentage, etc.		
	When the percentage is calculated, the number of patients of		
Catanania 1 data	"unknown" and "not provided" is included in the denominator. Chapter		
Categorical data	13 stipulates the details regarding the setting of denominators.		
	The patients of "unknown" and "not provided" are excluded in the		
	statistical test.		
0 (1)	Number of patients, mean, standard deviation, median, minimal value,		
Quantitative data	maximal value, etc.		

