	When "smoking" is checked among the items for smoking history in
	the survey form, or when any descriptions are made in the smoking
	period of "smoking", they should be classified as "smoking". When
Detailed classification of	"in the past" is checked or any descriptions are made in the smoking
	period "in the past" in patients who are not classified as "smoking",
smoking history	the case should be classified as "only in the past (not smoking now)".
	When "with smoking" is checked but nothing is checked in the
	detailed classification, or when "unknown" is checked, they should
	be "unknown".
Patients with dosing	Patients other than those who satisfied [1] to [4] of "Administration
deviation of Humira	status (dosage and administration)"
Presence/absence of	When "Self-administration" in the "Administration status of Humira"
self-administration	column is checked at least once, the case should be classified as
	"with" self-administration. Others are "without" self-administration.

Data name	Derivation and calculation methods
	When both "administration by physician" and "self-administration"
	are checked, the case should be "with self-administration".
	When "with" self-administration error is checked in the survey form,
	it should be classified as "with" the error. When "without" is
D / 1 C	checked, it should be "without" the error.
Presence/absence of	When some details are provided along with the onset date in the
self-administration error	self-administration error column irrespective of a check on
	"with"/"without", it should be regarded as "with" the error.
	If nothing is described there, it should be "unknown/not provided".
	It should be identified based on the sex in the patient's information of
G.	the survey form. When multiple items are checked or data without a
Sex	description are included, the case should be classified as
	"unknown/not provided".
	It should be identified based on pregnancy/nursing in the patient's
	information of the survey form. When multiple items are checked or
D / ·	data without a description are included even if the sex has been
Pregnancy/nursing	selected as "woman", the case should be classified as "unknown/not
	provided". If the sex is not "woman" even though a description has
	been made for this item, it is excluded from the calculation.
	It should be identified based on the race in the registration form.
Race	When multiple items are checked or data without a description are

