	Not conducted: other than the above
Presence/absence of prior	The drug names described in "prior-medication history for colitis
medications	ulcerative" in the survey form should be regarded as the prior

Data name	Derivation and calculation methods
	medications. Note that when a drug code is null, it is not regarded as a prior medication. When prior-medication data are contained in the survey form, it
Presence/absence of prior medication (aminosalicylic acid	when prior-medication data are contained in the survey form, it should be classified as "with prior medication". When there is no description of "presence/absence of prior medications" in the survey form or the assessment is impossible, it should be classified as "unknown/not provided", and other cases are "without prior medications". Refer to "171218 drug list_UC". If prior-medication data of the applicable drug code are provided in the survey form, or if an aminosalicylic acid drug in the survey form is checked, regard the case as "with aminosalicylic acid". Others are "without
drug)	aminosalicylic acid". Refer to "171218 drug list UC". If prior-medication data of the
Presence/absence of prior medication (corticosteroids)	applicable drug code are provided in the survey form, or if corticosteroids in the survey form is checked, regard the case as "with corticosteroids". Others are "without corticosteroids".
Presence/absence of prior medication (azathioprine)	Refer to "171218 drug list_UC". If prior-medication data of the applicable drug code are provided in the survey form, or if azathioprine in the survey form is checked, regard the case as "with azathioprine". Others are "without azathioprine".
Presence/absence of prior medication (6-mercaptopurine)	Refer to "171218 drug list_UC". If prior-medication data of the applicable drug code are provided in the survey form, or if 6-mercaptopurine in the survey form is checked, regard the case as "with 6-mercaptopurine". Others are "without 6-mercaptopurine".
Presence/absence of prior medication (azathioprin & 6-mercaptopurine)	Refer to "171218 drug list_UC". If prior-medication data of the applicable drug code are provided in the survey form, or if azathioprin and 6-mercaptopurine in the survey form are checked, regard the case as "with azathioprin & 6-mercaptopurine". Others are "without azathioprin & 6-mercaptopurine".

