Presence/absence of prior medication (tacrolimus & ciclosporin)	Refer to "171218 drug list_UC". If prior-medication data of the applicable drug code are provided in the survey form, or if tacrolimus & ciclosporin in the survey form is checked, regard the case as "with tacrolimus & ciclosporin". Others are "without tacrolimus & ciclosporin".
Presence/absence of	Refer to "171218 drug list_UC". If prior-medication data of the

Data name	Derivation and calculation methods
prior medication	applicable drug code are provided in the survey form, or if antibiotics
(antibiotics)	in the survey form is checked, regard the case as "with antibiotics".
	Others are "without antibiotics".
	When any items other than biological products in the survey form are
	checked, and when prior medication data on the drug code applicable
Presence/absence of	to the drug other than aminosalicylic acid drug, corticosteroids,
prior medication (others)	azathioprine, 6-mercaptopurine, tacrolimus, ciclosporin and
	antibiotics are included in reference to "171218 drug list_UC",
	regard it as "with others". Other cases are "without others".
Presence/absence of	Refer to "171218 drug list_UC". If prior-medication data of the
	applicable drug code are provided in the survey form, or if Infliximab
prior medication (Infliximab)	in the survey form is checked, regard the case as "with Infliximab".
(IIIIIXIIIIau)	Others are "without Infliximab".
	When 'biological products' is checked in the survey form, and when
Presence/absence of	prior-medication data of the drug codes other than Infliximab are
prior medication (other	provided in the survey form in reference to "171218 drug list_UC",
biological products)	regard the case as "with other biological products". Others are
	"without other biological products".
	The cases with either "with prior medication (Infliximab)" or "with
	prior medication (other biological products)" are regarded as "with a
Presence/absence of	treatment history with biological products". Others are "without a
treatment history with	treatment history with biological products".
biological products	As for presence/absence of the history by 'detailed classification
biological products	"with" biological products', if the applicable data among
	"Infliximab" and "other biological products" are contained, the case
	is regarded as "with" the history. Others are "without" the history.
	When the description is made in "Prior treatment for colitis ulcerative

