discontinuation, other	the condition improved, the condition worsened
reasons	Poor adherence, for study
Sex	Man, women, unknown/not provided
Pregnancy/nursing	Not pregnant/nursing, pregnant, nursing, unknown/not provided
Race	Japanese, other Asians, others, unknown/not provided
Age (in years)	$<15, \ge 15$ and $<65, \ge 65$, unknown/not provided
	<30, ≥30 and <40, ≥40 and <50, ≥50 and <60, ≥60, unknown/not
Body weight (kg)	provided
BMI(kg/m ²)	$<18.5, \ge 18.5 \text{ and } <25, \ge 25 \text{ and } <30, \ge 30, \text{ unknown}$
Duration of illness (in	
years)	$<2, \ge 2$ and $<10, \ge 10$, unknown/not provided
Indication (registration	Colitis ulcerative, others, not provided
form)	

Data	How to stratify
Allergy history	Without the history, with the history, unknown/not provided
Smoking history	Without the history, with the history, unknown/not provided
Detailed classification of smoking history	Smoking, only in the past (not smoking now), unknown
Tuberculosis test	Not conducted, conducted
Hepatitis B test	Not conducted, conducted
Complications	Without the history, with the history, unknown/not provided
Detailed classification of complications	Liver disorder, renal disorder, blood disorder, respiratory disorder, others
Other classification of complications	Diabetes mellitus, osteoporosis, malignant tumour, others
Medical history	Without the history, with the history, unknown/not provided
Detailed classification of medical history	Tuberculosis, non-tuberculous mycobacteriosis, interstitial pneumonia, bronchitis bacterial, aplastic anaemia, pancytopenia, malignant tumour, others
Prior medications for colitis ulcerative	Without the history, with the history, unknown/not provided
Details classification of	Infliximab, other biological products, aminosalicylic acid products,
prior medications for	corticosteroid, azathioprine & 6-mercaptopurine, tacrolimus &
colitis ulcerative	ciclosporin, antibiotics, prior medication: others
Prior treatment for colitis ulcerative	Without the history, with the history, unknown/not provided
Details classification of prior treatment for colitis ulcerative	Leukocytapheresis, surgery, enteral nutrition therapy, intravenous nutrition therapy, others
Treatment history with biological products	Without the history, with the history, unknown/not provided

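### Blank biologic-history and self-administration entries are coded 'without', so the 'unknown/not provided' class that SAP Section 11 lists for both variables can never be filled

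*SAP*

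**What the plan says.** **Derivation (SAP 10.1 General).** Biologic history is 'with' if the infliximab flag or the other-biologics flag is positive. The rule then closes the list: "treatment history with biological products'. Others are 'without a" treatment history. The infliximab flag has the same default ("Others are 'without Infliximab"), as does the detailed classification by product ("Others are 'without' the history"). Self-administration is 'with' if its box is ticked at least once; after that, "Others are 'without' self-administration". None of these rules has a branch for a blank or unassessable entry.

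**Strata (SAP Section 11).** Treatment history with biological products and self-administration each have three classes: "Without the history, with the history, unknown/not provided".

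**Handling of unknowns.** SAP 9.2 says "The patients of 'unknown' and 'not provided' are excluded in the" statistical test, and 9.5 repeats the exclusion.

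**Neighbouring rule.** For prior medications as a whole, SAP 10.1 does provide the branch. Where the form does not describe their presence or absence, "or the assessment is impossible, it should be classified as 'unknown/not provided', and other cases are 'without prior medications". Prior treatment is handled the same way.

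**Data collected (Protocol Section 8).** The enrolment form records use history of biological products, and the CRF records presence or absence of prior anti-TNFα treatment.

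**The concern.** Sections 10.1 and 11 cannot both be carried out for these two variables. Section 11 requires a class that the 10.1 derivation never produces. Because the recoding happens first, the exclusion of unknowns in 9.2 and 9.5 has nothing to act on, and a blank is analysed as a confirmed negative.

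The result is inconsistent within a single table. A patient whose prior-medication section is blank is 'unknown' for prior medication and leaves that test. The same patient is a true negative for biologic history, which is also a listed factor in Tables 2.9, 3.4 and 3.4.1. In the descriptive Table 2.18 this patient is counted as 'without'.

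The relation of safety and effectiveness to anti-TNF or biologic experience is a named analysis item in both documents. The plan expects the unexposed group to be the smaller one by 4 to 1, so misplaced exposed patients weigh more heavily there than they would in the larger group. Since no output can show the unknown count, a reader of the report could not judge whether this matters.

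**Working it through.** **Step 1: rules side by side.**

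| Variable | SAP 10.1: blank entry becomes | SAP 11: unknown class listed |
|---|---|---|
| Prior medications (parent) | unknown/not provided | yes |
| Prior treatment (parent) | unknown/not provided | yes |
| Biologic history | without | yes: conflict |
| Self-administration | without | yes: conflict |
| Single prior drugs, single complications | without | no: no conflict |

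The conflict is therefore confined to two variables.

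**Step 2: the plan's own figure.** Inputs from Protocol Section 2 and SAP 4.3 are 1500 patients, 70% dropout, 30% without a Mayo score, 80:20 anti-TNF experienced to naive, and Week 52 remission of 10% and 30%.

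- 1500 × 0.30 = 450; 450 × 0.70 = 315; 315 × 0.20 = 63 naive; 315 × 0.80 = 252 experienced.
- Naive 95% CI half-width, normal approximation with continuity correction: 1.96 × √(0.30 × 0.70 / 63) + 1/(2 × 63) = 0.113 + 0.008 = 0.121. This gives 17.9 to 42.1, as printed in Table 2.

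**Step 3: effect of the default.** Let m be the share of all patients with a blank history and q the share of those who are truly exposed. Neither is in the documents.

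- 'Without' group as coded, as a share of all patients: 0.20 + qm
- Exposed share of that group: s = qm / (0.20 + qm)
- Apparent difference, using 30% and 10% for illustration: 20 × (1 − s) points

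| m | q = 0 (all blanks naive) | q = 0.8 (blanks unrelated to history) | q = 1 (all blanks exposed) |
|---|---|---|---|
| 2% | s = 0; 20 points | 0.016/0.216 = 7.4%; 18.5 points | 0.02/0.22 = 9.1%; 18.2 points |
| 5% | s = 0; 20 points | 0.040/0.240 = 16.7%; 16.7 points | 0.05/0.25 = 20.0%; 16.0 points |
| 10% | s = 0; 20 points | 0.080/0.280 = 28.6%; 14.3 points | 0.10/0.30 = 33.3%; 13.3 points |

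At q = 0.8 the apparent remission rate in the 'without' group is 28.5%, 26.7% or 24.3%. With 315 assessed patients, power for the difference (two-sided 5%) falls from 95.7% to 94.4%, 92.1% or 87.6%. With 1500 patients it stays at about 100%, so the harm there would be bias only.

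**Step 4: after the fix.** If blankness is unrelated to outcome within each history group, the difference stays at 20 points. At q = 0.8 the naive group falls from 63 to 61.7, 59.8 or 56.7, with half-widths of 12.2, 12.5 or 12.8 points. At q = 0 it falls to 63 − 315m = 56.7, 47.3 or 31.5.

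**Related route.** The other-biologics flag asks for a ticked box and a drug code. If both are required, and given "Note that when a drug code is null, it is not regarded as a prior medication", a patient with the biologics box ticked but no usable code also falls to 'without'.

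**The case against.** Section 9.1 lets Chapter 10 define handling item by item, so a default to 'without' is not in itself a breach of the no-imputation rule. That stands; the firm conflict is with Section 11.

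Blanks may also be rare. History is collected on two forms, forms are checked, rechecked and reinvestigated, and unconfirmed or inconsistent cases leave the safety set. This makes a low missing share plausible but does not establish one. At 2% missing the shift is at most 1.8 points in the table above, well inside the planned half-width of 12.1.

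A reader might infer several stronger things that the documents do not support:

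- *That the naive group is contaminated.* This requires some blanks to be truly exposed. A blank may simply mean no use, and then there is no contamination.
- *That the shrunken differences are the expected error in the cited tables.* The 10% and 30% are Week 52 full Mayo remission rates by anti-TNF history. Tables 2.9 and 2.18 report adverse reactions, 3.4 general improvement, and 3.4.1 partial Mayo remission at final assessment. Table 2.18 specifies no test, and the SAP variable is biologic history, which only approximates anti-TNF history. The group of 63 is also specific to the Week 52 Mayo score; the plan implies about 300 naive patients overall (1500 × 0.20).
- *That every item defaulting to 'without' is wrong.* Section 11 lists no unknown class for single prior drugs or single complications, and their parent variables already have one.
- *That this is the plan's leading comparison.* It is one of several named items and one of more than 50 background factors.

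**Conclusion.** The mismatch is certain from the text and affects two variables, biologic history and self-administration. As written, the unknown class is always empty, the missing share is hidden, and blank records enter the tests as true negatives despite 9.2 and 9.5.

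The consequence is conditional. It is nil if all blanks are truly unexposed. It is small at 1–2% missing. It is material at about 10% missing if blanks are unrelated to history, when some 29% of the 'without' group would be exposed and an illustrative 20-point difference would read as 14.3. These sizes rest on the plan's 80:20 mix, on assumed missing shares, and on an assumption about whose history is missing. The documents settle neither of the last two. No comparable size can be given for self-administration, because the documents give no expected split or rates for it.

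The derivation should be corrected, because otherwise the report itself could not show which of these cases applies.

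**What to change.** In SAP 10.1, for these two variables only:

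- **Biologic history:** 'with' on any positive entry; 'without' only when the form says so, using the anti-TNFα presence/absence and biologic-history fields already collected; 'unknown/not provided' when the item is blank or not assessable, following the prior-medications rule. A ticked biologics box without a usable drug code should not become 'without'.
- **Self-administration:** 'with' if ticked at least once; 'without' only when the recorded administration category shows it; 'unknown/not provided' when the category is blank.

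Report the unknown counts in Tables 1.12 (biologic history) and 1.13 (self-administration), and apply 9.2 and 9.5 as written. A sensitivity run that counts unknowns as 'without' would show whether the choice matters. Single prior drugs and single complications stay as they are.

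**Cost:** one line per variable. Patients with unknown status leave the corresponding tests. The naive group shrinks only slightly if blanks are unrelated to history (63 to 59.8 at 5% missing), but more if blanks are mostly naive (to 47.3 at 5% if all are), which is the reason for the sensitivity run.
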